1. INTRODUCTION

The purpose of this reporting and analysis plan (RAP) is to describe the analyses to be included in the Clinical Study Report for Protocol 200879.

2. SUMMARY OF KEY PROTOCOL INFORMATION

This study will be undertaken in participants who present with an acute moderate or severe exacerbation of COPD requiring Standard of Care (SoC), referred to as the index exacerbation.

2.1. Study Objective(s) and Endpoint(s)

Objectives	Endpoints
Primary Objectives	Primary Endpoints

 To characterise the dose response of nemiralisib administered in addition to SoC compared with placebo and SoC in participants diagnosed with an acute moderate or severe exacerbation of COPD 	
 Change from baseline in Clinic Visit trough forced expiratory volume in one second (FEV₁) at Day 84 measured post-bronchodilator
Secondary Objectives	Secondary Endpoints

 To characterise the dose response and efficacy of nemiralisib administered in addition to SoC compared with placebo and SoC in participants diagnosed with an acute moderate or severe exacerbation of COPD 	
 Rate of moderate and severe exacerbations over the 12-Week Treatment Period Time to next moderate/severe exacerbation following index exacerbation Change from baseline in Clinic Visit trough FEV₁ measured pre- and post-bronchodilator at Days 14, 28, 56, and 84 (Day 84: post-bronchodilator is the primary endpoint; pre-bronchodilator is a secondary endpoint) and at hospital discharge (only for participants who are hospitalized for the index exacerbation) Change from hospital discharge in clinic visit trough FEV₁ measured pre- and post-bronchodilator at Days, 14, 28, 56, and 84 (in participants hospitalized for index exacerbation only)

 To evaluate the treatment effect of nemiralisib in addition to SoC compared with placebo and SoC on symptoms indicative of an exacerbation and on health status using Patient-Reported Outcomes (PROs) in participants diagnosed with an acute moderate or severe exacerbation of COPD 	
EXAcerbations of Chronic Pulmonary Disease Tool (EXACT-PRO)
 
 Proportion of participants achieving the EXACT definition of recovery from the index exacerbation by Days 14, 28, 56, and 84 Time to recovery from index exacerbation Severity of subsequent HCRU-defined exacerbation(s) defined by EXACT 
COPD Assessment Test (CAT)
 
 Proportion of responders using the CAT at Treatment Days 28, 56, and 84, and following EXACT defined

Objectives	Endpoints
	
recovery from the index exacerbation
 
 Change from baseline (Day 1) in CAT total score at Days 28, 56, and 84 and following EXACT defined recovery from the index exacerbation 
St. George's Respiratory Questionnaire (SGRQ) Total Score
 
 Proportion of responders on the SGRQ total score as measured by the SGRQ for COPD Patients (SGRQ-C) at Days 28, 56, and 84 Change from baseline (Day 1) in SGRQ total score at Days 28, 56, and 84

 To evaluate the usage of rescue medication in patients diagnosed with an acute moderate or severe exacerbation of COPD 	
 Rescue medication use (occasions/day), averaged over each week of treatment and over the 84-day treatment period The percentage of rescue-free days (24-hour periods) during each week of treatment and over the 84-day treatment period

 To evaluate the population pharmacokinetics of nemiralisib in participants diagnosed with an acute moderate or severe exacerbation of COPD 	
 Plasma nemiralisib concentrations and derived PK parameters (e.g., area under the curve [AUC (0-24) and AUC(0-t)], maximum concentration [C_{max}], time at maximum concentration [T_{max}], C_{trough}) as appropriate will be collected in a subset of randomized participants (approximately 300) at selected sites as follows: trough (pre-dose) for the study treatment and post-dose for the study treatment from 0-1 hour and >1 to 6 hours on Days 14 and 28 of the 12-Week Treatment Period

 To assess the safety and tolerability of nemiralisib and placebo in participants diagnosed with an acute moderate or severe exacerbation of COPD 	
 Incidence of adverse events (AEs; including serious AEs and AE of Special Interest [AESI]) Vital signs (pulse rate, systolic and diastolic blood pressure) (measured at each clinic visit up through Visit 7 [Day 112] or Early Withdrawal Visit) 12-lead electrocardiogram (ECG) assessments (performed at clinic Visits 1 [Screening], 3 [Day 14], 6 [Day 84], and 7 [Day 112] or Early Withdrawal Visit) Clinical laboratory tests (hematology and chemistry; performed at each clinic visit up through Visit 7 [Day 112] or Early Withdrawal Visit) Incidence of COPD exacerbations
Exploratory Objectives	Exploratory Endpoints

 To further characterize the dose response, and efficacy, of nemiralisib administered in addition to SoC compared with placebo and SoC in participants diagnosed with an acute moderate or severe exacerbation of COPD 	
 Rate of mild exacerbations over the 12-Week Treatment Period Rate of all exacerbations (mild, moderate and severe combined) over the 12-Week Treatment Period Time to next exacerbation (mild, moderate and severe combined)

Objectives	Endpoints

 To evaluate the treatment effect of nemiralisib in addition to SoC compared with placebo and SoC on symptom stability following an exacerbation using Patient-Reported Outcomes in participants diagnosed with an acute moderate or severe exacerbation of COPD 	
 Stability of symptoms post recovery measured using E-RS:COPD (Evaluating Respiratory Symptoms in COPD) and subscales from Randomization (Visit 2) to Day 84 (Visit 6)

 To explore the PK/PD relationship for nemiralisib 	
 Relationship between drug exposure and Pharmacodynamic responses (e.g. efficacy, heart rate, clinical laboratory analytes and blood biomarkers) in the PK subset of participants (approximately 300) at selected sites

 To evaluate the treatment effect of nemiralisib in addition to SoC compared with placebo and SoC on HCRU in participants who experience a severe exacerbation of COPD 	
 Measures of HCRU related to severe exacerbations (e.g., hospitalizations, length of hospital stay, re-hospitalization within 30 days, number of Emergency Room [ER] visits, etc.)

 To evaluate compliance with study treatment 	
 Number of actuations of the double-blind study treatment as measured by the clip-on Propeller Sensor (for countries where the Propeller Sensor for ELLIPTA is available)

 To evaluate inflammatory markers in blood in relation to acute exacerbation of COPD 	
 Blood samples collected at Screening through Visit 7 (as part of the clinical laboratory blood samples) for analysis of blood eosinophil counts and inflammatory mediators Blood samples for analysis of inflammatory biomarkers (including but not limited to: high sensitivity C-reactive protein [hs-CRP], chemokine interferon-γ inducible protein 10 kDa (CXCL10)), and procalcitonin) collected at Visit 1 (Screening)

 To evaluate inflammatory and infective markers in sputum in relation to acute exacerbation of COPD 	
 Spontaneous sputum sample for analysis of inflammatory and infective markers collected at Screening/Day 1 (pre-dose) and Day 56 in participants who are willing and able to provide a sample

 To evaluate the potential post-treatment impact of double-blind study treatment during the 12-Week Post-Treatment Follow-Up Period 	
 Change from baseline (Day 84) in Clinic Visit trough FEV1 measured pre- and postbronchodilator at Day 112, 140 and 168 Rate of moderate and severe COPD exacerbation(s) during the 12-Week Follow-Up Period Rate of moderate and severe COPD exacerbation(s) over the 24 week study duration Time to next exacerbation following cessation of double blind study treatment Proportion of responders using the CAT at Days 112 and 168 Change from baseline (Day 1) in CAT Total score at Days 112 and 168 Proportion of responders on the SGRQ Total Score as measured by the SGRQ-C at Days 112 and 168 Change from baseline (Day 1) in SGRQ total score at

Objectives	Endpoints
	Days 112 and 168 
 • Severity of subsequent HCRU exacerbation defined by EXACT • E-RS: COPD and subscales from last dose of double-blind study treatment • Rescue medication use up to Day 112

2.2. Study Design

This is a Phase IIb, multicenter, randomized, stratified (by index COPD exacerbation severity [moderate or severe] and by whether or not the participant is in the PK Subgroup), double-blind (Sponsor Open), placebo-controlled, parallel-group study in participants who present with an acute moderate or severe exacerbation of COPD requiring Standard of Care (SoC).

This study consists of a Screening Period, a 12-Week Treatment Period and a 12-Week Post-Treatment Follow-Up Period. Randomization and the first dose of the double-blind study treatment administration (Visit 2/Day 1) should take place in the morning, as soon as possible following determination of eligibility and completion of the baseline measures, including the EXACT-PRO questionnaire for the day of randomization, and FEV₁ measurement and no later than 48 hours after the start of SoC.

PK Subgroup: Sparse PK sampling will be conducted in a subgroup of participants at selected sites. The PK Subgroup will be identical to the main study in terms of the study population, design, and conduct, with the exception of blood draws (3 per visit on Days 14 and 28) for PK analysis.

3. PLANNED ANALYSES

3.1. Interim Analyses

Ongoing data reviews of unblinded safety data, conducted by an Internal Safety Review Committee (iSRC), will be performed throughout the trial. Details will be documented in the iSRC charter.

Interim analyses of the primary endpoint and key secondary endpoints to inform internal decision making will be conducted periodically throughout the trial. The first analysis (Interim Analysis 1) is planned to occur when approximately 170 participants complete 28 days of treatment, where approximately 50 of the 170 participants have an index exacerbation defined as severe. A change that could arise from this interim analysis is a specification of the stratification proportions by index exacerbation severity status (moderate or severe). This decision will be based on inspection of all available endpoints at the interim analysis.

Further interim analyses will be performed, depending on the observed recruitment rate. At least one interim analysis of the primary endpoint of change from baseline in clinic visit trough FEV₁ at Day 84 measured post-bronchodilator will be performed to

determine whether or not any adjustments to the randomization ratio across doses would help optimize the characterization of the dose response profile for nemiralisib. This analysis (Interim Analysis 2) is planned to occur when approximately 300 participants complete 84 days of treatment or when approximately 400 participants remain to be randomized, whichever occurs first. Adjustments could include ceasing randomization to an existing dose(s) of nemiralisib and/or modification of the allocation ratios for the existing nemiralisib doses and/or addition of a 25mcg dose. Other changes may include specification of the stratification proportions by index exacerbation severity status.

An interim analysis of efficacy and safety data collected during the Double-Blind Treatment Period will be conducted when the last participant in the study has completed the 12-week Double-Blind Treatment Period (End of Treatment Interim Analysis). The aim of this analysis is to provide GSK with timely data to inform internal decision making, prior to the end of study.

The following table describes the endpoints that will be analysed/summarised at each interim:

Interim	Purpose of interim	Endpoints
Interim Analysis 1	To inform internal decision making	
 • Change from baseline in FEV₁ at Days 14, 28, and 56 measured pre- and post-bronchodilator • Other spirometry measures (percent predicted FEV₁, Forced Vital Capacity (FVC), percent predicted FVC and FEV/FVC ratio • On-treatment exacerbations • Proportion of participants achieving EXACT-defined recovery by Days 14, 28, 56 and 84

Interim	Purpose of interim	Endpoints
Interim Analysis 2	To determine if any adjustments to the randomization ratio would help characterize the dose response profile for nemiralisib	Endpoints listed for Interim Analysis 1 and also: 
 • Change from baseline in FEV₁ at Day 84 measured pre- and post-bronchodilator • Rate of (on-treatment) exacerbations over the 12-Week Treatment Period • Time to next (on-treatment) exacerbation during the 12-Week Treatment Period • Proportion of responders using the CAT • Change from baseline in CAT Total Score • Proportion of responders using the SGRQ • Change from baseline in SGRQ Total Score • Rescue medication use, as measured in eDiary
End of Treatment Interim Analysis	To inform internal decision making	Selected Efficacy and Safety endpoints as defined in Appendix 11: List of Data Displays

The statistical methods of analyses are described in Section 7.

The Respiratory Data Sciences Group will apply machine learning techniques to the interim data to determine if identifiable phenotypic sub-population(s) of COPD participants are present at baseline, and if they result in different responses to Nemiralisib, to predict which participants will respond to Nemiralisib therapy, and to identify/quantify relationship(s) between different endpoints and response measures. Details of these analyses will be described in a separate RAP and results will be reported separately to the Clinical Study Report (CSR).

The following functions will be unblinded to interim analysis data: Clinical Statistics, Clinical Programming and Respiratory Data Sciences Group. Other member of GSK will be unblinded to group level summary data following the interim analyses (as documented internally).

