5. CONSIDERATIONS FOR DATA ANALYSES AND DATA HANDLING CONVENTIONS

5.1. Study Treatment & Sub-group Display Descriptors

Treatment Group Descriptions			
RandAll NG Randomization System		Data Displays for Reporting	
Code	Description	Description	Order in TLF
A	Placebo	Placebo	1
B	GSK2269557 12.5 mcg	NEMI 12.5 mcg	2
C	GSK2269557 25 mcg*	NEMI 25 mcg	3
D	GSK2269557 50 mcg	NEMI 50 mcg	4
E	GSK2269557 100 mcg	NEMI 100 mcg	5
F	GSK2269557 250 mcg	NEMI 250 mcg	6
G	GSK2269557 500 mcg	NEMI 500 mcg	7
H	GSK2269557 750 mcg	NEMI 750 mcg	8

* The nemiralisib dose of 25 mcg may be added following the results of an un-blinded interim analysis if further characterization of the lower end of the dose response curve is required.

Treatment comparisons will be displayed as follows using the descriptors as specified:

1. NEMI 12.5 mcg vs Placebo
2. NEMI 25 mcg vs Placebo
3. NEMI 50 mcg vs Placebo
4. NEMI 100 mcg vs Placebo
5. NEMI 250 mcg vs Placebo
6. NEMI 500 mcg vs Placebo
7. NEMI 750 mcg vs Placebo

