The posterior median change from baseline with 95% Highest Posterior Density (HPD) Credible Intervals, will be presented for each dose along with the adjusted median difference from placebo with 95% HPD, calculated at the mean baseline value across the treatment arms. Posterior probabilities that the true improvement is greater than 0 mL and 75 mL will also be presented. Graphical representation of the dose response across the full dose range will also be produced to allow inference to be made for the non-studied doses based upon the model fit.

For the futility analysis:

The predictive probability of success at the end of the study will be calculated (assuming the randomisation ratios remain the same after the interim) for each dose using the formula suggested by [Spiegelhalter, 2004](#) as follows:

$$\text{Predictive probability} = 1 - \Phi \left[\frac{\sqrt{n_1}}{\sqrt{m_1}} z_{0.95} - \sqrt{\frac{n_1 + m_1}{m_1}} \frac{y_n}{\sigma} \right]$$

Where n_1 is the number of subjects with Day 84 data in the active arm of interest, m_1 is the number of subjects yet to be observed in the active arm of interest, y_n is the posterior mean difference from placebo from the fitted model, and σ is the standard deviation of the posterior mean difference from placebo.

For the possible adaptations at Interim Analysis 2:

If the study is not deemed futile, and either the 4 parameter or 3 parameter E_{\max} dose response curves has successfully been fitted to the data then adaptation of the randomisation schedule will be considered, to drop, add or amend doses from the randomisation scheme.

The adaptation will be done by comparing the relative information from alternative randomisation schemes with the original randomisation schemes, such to find the design

that provides the most information about the dose response relationship. The efficiency ratio (ER) for an alternative scheme compared to the original, will be calculated as:

$$ER(\theta_i) = \left(\frac{|M(\xi_1, \theta_i)|}{|M(\xi_F, \theta_i)|} \right)^{\frac{1}{p}}, i=1, \dots, 1000$$

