7.2.1.1. Statistical analyses

The rate of exacerbations will be analysed using a Bayesian generalized linear model assuming a negative binomial distribution for the underlying exacerbation rate with a log link function. An offset to account for the length of time on treatment or in study, depending on the specified time-period, for each participant (as described above) will be included in the model as \log_e (length of time).

Non-informative priors will be used for all modelling parameters. Wherever possible conjugate priors will be utilised.

The median exacerbation rates for each dose arm per 12 weeks, along with the median ratio in exacerbation rates (nemiralisib/placebo) per 12 weeks for each dose, will be estimated and corresponding 95% HPD credible intervals presented. The probability that the true exacerbation rate ratio is less than 1, in addition to other values appropriately selected based on the data, will be presented.

Based on pharmacological predictions, the 500 mcg and 750 mcg doses are expected to result in similar levels of target inhibition and thus potentially translate to similar clinical benefit, therefore estimates of the exacerbation rates for pooled data from 500 mcg plus 750 mcg will also be presented.

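### If Interim Analysis 2 changes the randomisation schedule, the final models pool placebo across both stages with no stage term, and index severity enters them only at discretion

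*SAP*

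**What the plan says.** Section 3.1 places Interim Analysis 2 at "approximately 300 participants complete 84 days of treatment or when approximately 400 participants remain to be randomized, whichever occurs first". On what may follow, it says: "Adjustments could include ceasing randomization to an existing dose(s) of nemiralisib and/or modification of the allocation ratios for the existing nemiralisib doses", then "and/or addition of a 25mcg dose. Other changes may include specification of the stratification proportions by index exacerbation severity status". Section 7.1.2 gives five example designs. All five change the set of doses, and three of them add 25 mcg.

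Section 5.1 confirms that "The nemiralisib dose of 25 mcg may be added following the results of an un-blinded interim analysis" and lists 25 mcg against placebo among the comparisons to be displayed. Efficacy is analysed in the MITT population (Section 4), meaning everyone randomised and dosed, with a single placebo group.

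The model terms are as follows.

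- **Dose-response (7.1.2):** one common E0, an Emax part, and baseline terms on each. Results for each dose are given "along with the adjusted median difference from placebo with 95% HPD, calculated at the mean baseline value across the treatment arms".
- **Repeated measures (7.1.3):** baseline-by-Day and treatment-by-Day.
- **Exacerbation rate (7.2.1.1):** negative binomial with a log-time offset, reporting arm rates "along with the median ratio in exacerbation rates (nemiralisib/placebo) per 12 weeks for each dose".
- **Cox (7.2.2.1) and logistic (7.2.5.4):** no period term named.

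The covariate table in 5.4.1 has no stage or calendar-time variable. Index severity is named there as a key covariate, but whether any covariate is included depends on its effect on fit or convergence. Section 7.1.2 also lets covariates be removed if the dose-response model does not converge.

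**The concern.** Once the schedule changes, dose and time of randomisation are no longer independent. Everyone on 25 mcg would be randomised late, everyone on a dropped dose early, and placebo would span both stages. A model without a stage term reads any difference between the stages as part of the dose effect. The season, the mix of sites and the standard of care can all move exacerbation rates and FEV1 recovery over a recruitment period. The plan adds a route of its own, because the severity proportions may be reset at the same interim.

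The affected contrasts include those for 25 mcg, a dose that Section 5.1 says would be added to characterise the lower end of the curve. Covariate selection by fit does not protect them. A term that is needed because allocation depends on stage should be fixed in advance, not kept or dropped according to how well the model fits.

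**Working it through.** The SAP gives no sample size, SD or allocation ratio, so there is no figure of its own to reproduce. Everything marked assumed below is an illustration under a true null.

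**Inputs**
- p, the share of placebo randomised before the change: assumed 0.4-0.6.
- r, the background exacerbation rate after the change divided by the rate before: assumed.
- Severe share before the change: 50/170 = 29.4%, from Section 3.1 on Interim Analysis 1 ("approximately 50 of the 170 participants have an index exacerbation defined as severe").
- FEV1 drift between stages: assumed 50 mL. SD 240 mL, 200 on placebo and 50 on 25 mcg: assumed.
- FEV1 benchmark: more than 90% posterior probability of a difference above 0 (Section 3.1.1.1). With flat priors this is met 10% of the time per comparison under the null.

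**1. Exacerbation rate, 25 mcg against pooled placebo.** Spurious rate ratio = r / (p + (1 − p)r).
- p = 0.6, r = 0.7: 0.7/0.88 = 0.795
- p = 0.4, r = 0.8: 0.8/0.88 = 0.909
- p = 0.4, r = 1.25: 1.25/1.15 = 1.087
- p = 0.6, r = 1.4: 1.4/1.16 = 1.207

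**2. FEV1, arm by arm.** Bias = (share of the dose randomised after the change − the same share in placebo) × drift.
- 25 mcg: p × 50 mL, which is 25 mL at p = 0.5 and 30 mL at p = 0.6.
- Dropped dose: −(1 − p) × 50 mL, which is −25 mL and −20 mL. It reaches about −29 mL in the design that drops 12.5 and 50 mcg, because placebo's later share then rises.
- Re-weighted dose: in between. If 60% of a dose and 50% of placebo fall after the change (assumed), the bias is 0.1 × 50 = 5 mL.

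With SE = 240 × √(1/200 + 1/50) = 37.9 mL, the chance that an inert 25 mcg dose passes the 90% benchmark is Φ(bias/SE − 1.282). That is 27% at p = 0.5 and 31% at p = 0.6, against 10% without drift. The range is 31-37% at SD 200 mL and 23-26% at SD 300 mL.

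**3. Severity mix, if severity is left out of the model.** Bias = p × (later severe share − 0.294) × difference between strata. For a later share of 50% and p = 0.5-0.6, the gap is 0.103-0.124. An assumed 50-150 mL difference between strata then gives 5-18 mL. For later shares of 40-60% the range is 3-28 mL. It disappears if severity is in the model.

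**4. Emax primary model.** Noise-free 3-parameter Emax fits were run with a 50 mL drift, four of the example designs, 50% or 60% of the trial randomised before the change, and two assumed allocations (equal, and placebo and 750 mcg at three times the other arms). The raw arm difference at 25 mcg, where it was added, was 23-32 mL. The fitted bias was at most about 3 mL at 25 mcg and at most 16 mL at any dose. With a stage term it was 0 mL at every dose. The 4-parameter and log-linear models were not run.

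**The case against.** The strongest reply is that much of this is already contained.

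- **Placebo.** A reader might infer that 25 mcg would be compared only with earlier placebo participants and that the randomised comparison is lost. The SAP does not support that. The permitted changes concern nemiralisib doses, and none of the five example designs drops placebo, so concurrent placebo would exist inside the pooled group. The contrast is contaminated by the earlier participants, not destroyed.
- **Severity.** A reader might also infer that severity is left unadjusted. It is a randomisation stratum and a key covariate. Separate dose-response models by severity are planned (7.1.4), as are treatment-by-severity terms for the rate, Cox, EXACT and CAT analyses. What stands is narrower: its inclusion in the main models is discretionary, and severity-specific models do nothing about calendar drift.
- **Primary curve.** It is tempting to say that drift would distort the low end of the primary dose-response curve. The Emax fits do not show that. Parameters shared across doses smooth out one arm's shift.
- **Conditionality.** The problem needs an adaptation. That requires no futility, a fitted Emax curve, a median efficiency ratio above 1.05 and a 10th percentile above 1. It also needs real drift or a real shift in severity mix.

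Section 5.4.1 does allow additional covariates, but it commits to none.

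**Conclusion.** The gap is certain on the text: no stage term, no restriction to concurrent placebo, and severity optional in the main models. Its consequences are conditional on a change of schedule and on drift or a shift in severity mix.

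Under the stated assumptions the arm-by-arm results could be materially off. The 25 mcg rate ratio could be 0.80-0.91 with a falling background rate, or 1.09-1.21 with one rising by 1.25-1.4. For FEV1, 25-30 mL of bias could arise from a 50 mL drift. Dropped doses are biased in the opposite direction and re-weighted doses less. The primary Emax analysis is affected much less. This merits a change to the SAP, but it does not call the primary analysis into question.

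**What to change.** Add to Section 7 that, if the randomisation schedule changes, every efficacy model includes two fixed terms: stage (randomised before or after the change) and index severity. Neither is subject to the fit-based rule in 5.4.1 or to removal for non-convergence under 7.1.2. In the repeated-measures model, stage enters as stage-by-Day. In the Emax and log-linear models, it is an additive shift on E0. Add a sensitivity analysis of 25 mcg against concurrently randomised placebo only.

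No new data are needed, because the randomisation date is already used in 13.5.1. The cost is a few parameters (one per post-baseline visit for stage-by-Day) and a modest loss of precision for the affected doses. Under the assumed sizes, the concurrent-only comparison raises the SE from 37.9 mL to 41.6 mL (p = 0.5) or 43.3 mL (p = 0.6), about 10-14%, and returns the false-success rate to 10%.
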